5.3 Efficacy Assessments

5.3.1 Micturition Diary

The micturition diary will be used to record the date and time of each micturition, incontinence episodes, urgency episodes, and voiding volume. Voiding volume will be recorded at Visits 2, and 5 only. The diary will also be used to record daily medication intake. The diary must be completed for at least 2 days in order to be included in the efficacy assessment for that visit.

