Night time is the period between after sleep onset time and the wake-up time the following day (micturitions at the same time as the wake-up time will be excluded). The diary must be completed for at least 2 consecutive days to allow assessment of night time frequency for at least 1 night. Any data collected before the wake-up time on the first day of diary completion and after the sleep onset time on the third day cannot be included in the assessment of night time frequency. Only those subjects whose symptoms were confirmed at baseline (Visit 2) will be analyzed.
If there is no nocturia episode on all evaluable night time in each visit, then the mean number of nocturia episodes/24 hours is equal to zero. Therefore if the mean number of nocturia episodes per 24 hours is “0” at baseline, this subject is excluded from the analysis.

- Mean volume voided per micturition
Calculation is similar to ‘micturition’, but sum urinary volumes where the volume voided is > 0 and where ‘Urinary incontinence’ is not indicated, rather than count the episodes. The denominator will be the number of micturitions where the volume voided is > 0 and where ‘urinary incontinence’ is not indicated. Only those subjects whose symptoms were confirmed at baseline (Visit 2) will be analysed.

- Total OABSS score
For each patient, OABSS total score will be the sum total of the score of each item (Questions 1-4).
- Subscale scores (daytime frequency, nighttime frequency, urgency and urgency incontinence) from OABSS score
For each patient, OABSS subscale scores will be the score of each item (Questions 1-4).
- Total IPSS score
For each patient, total IPSS score will be the sum total of the score of each item (Questions 1-7).
- Subscale scores (storage subscale, voiding subscale-1, voiding subscale-2 and quality of life item) and individual scores from IPSS score
For each patient, IPSS subscale scores will be calculated by following each formula. Storage subscale is derived as sum of scores for questions 2, 4, and 7. Voiding subscale-1 is derived as sum of scores for questions 3, 5, and 6. Voiding subscale-2 is derived as sum of voiding subscale-1 and the score for question 1.
For each patient, Individual scores and IPSS QoL score will be the score of each item (Questions 1-7 and quality of life item).

- Symptom Bother and Total Health-Related Quality of Life scores (Total HRQL scores), as assessed by OAB-q

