6.1.3 Exploratory Efficacy Endpoints

The exploratory endpoints will include the change from Baseline to post baseline and End of Treatment in:

- Hours of undisturbed sleep (HUS)

For each patient, hours of undisturbed sleep (HUS) will be calculated by visit and night. Only those subjects whose symptoms were confirmed at baseline (Visit 2) will be analyzed, therefore if IPSS Q7 score is “0” at baseline, this subject is excluded from the analysis.

HUS is calculated as time from sleep onset time to time of first micturition episode (the variable ‘Urinary incontinence’ or ‘Urgency’ is NOT indicated and after the time of sleep onset time) only if the diary completed for 3 consecutive days is available. On the other hand, for those subjects who have no micturition episode between after sleep onset time and wake up time, HUS is calculated as time from sleep onset time to wake up time.

If the interval between sleep onset time and wake up time is more than 24 hours, HUS will be calculated as follows:

HUS is calculated as time from sleep onset time to time of first micturition episode (the variable ‘Urinary incontinence’ or ‘Urgency’ is NOT indicated and after the time of sleep onset time) only if the diary completed for 3 consecutive days is available and the time of first micturition episode is before AM.5:59 of the next day of sleep onset. On the other hand, for those subjects who have no micturition episode between after sleep onset time and AM.5:59 of the next day, HUS is null.

- First nighttime voided volume

For each patient, urinary volume at the first nighttime (between after the time of sleep onset and wake up time + 30 minutes) will be calculated. Only those subjects whose symptoms were confirmed at baseline (Visit 2) will be analysed.

If the interval between sleep onset time and wake up time is more than 24 hours, first nighttime voided volume will be calculated as follows:

For each patient, urinary volume at the first nighttime (after the time of sleep onset and before AM.5:59 of the next day) will be calculated. On the other hand, for those subjects who have no micturition episode between after sleep onset time and AM.5:59 of the next day, urinary volume at the first nighttime is null. Only those subjects whose symptoms were confirmed at baseline (Visit 2) will be analysed.

- Subscale scores (coping, concern, sleep and social interaction) and individual scores from OAB-q scores

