7.4.3 Analysis of Exploratory Endpoints

The exploratory endpoints include actual value and the change from Baseline to post-baseline and End of Treatment in:

- HUS
- First nighttime voided volume
- Subscale scores (coping, concern, sleep, social interaction) and individual scores from OAB-q

Concerning actual value and the change from baseline to post-baseline of these endpoints, descriptive statistics will be calculated by treatment group at each visit and at the End of Treatment for FAS.

Mean (+/- SD) plot for actual value and change from baseline to post-baseline will be presented for FAS.

For HUS, similar analysis will be done only for those subjects who have at least one micturition episode between sleep onset time and wake up time at baseline (e.x., IPSS Q7 > 0) or/and post-baseline. Descriptive statistics for HUS will be derived as the average of 2 consecutive nighttime diary. For example, if subject has only one night time episode in the 2 consecutive nighttime diary, average of HUS (time from sleep onset time to time of

first micturition episode) and HUS (time from sleep onset time to wake up time) will be calculated.

Kaplan-Meier curves will also be used to estimate the distribution of HUS for FAS. Median duration will be estimated using the corresponding 50th percentile of Kaplan-Meier estimates. A two-sided 95% confidence interval will be provided for this estimate. The 25th and 75th percentiles of Kaplan-Meier estimates, and the range of HUS (minimum, maximum) will be presented as well. The range will be determined including censored observations.

Conventions of censoring of HUS will be defined as; those subjects who have no micturition episode between sleep onset time and wake up time will be censored at wake up time. Also, similar analysis will be done treating them as subjects who have an event at the wake up time.

Radar charts of the mean of actual value for OAB-q will be made to present relationship between subscale scores by treatment group for FAS.

For individual score from OAB-q, frequency tabulations of scores will be presented for each treatment group at each visit and at the End of Treatment for FAS.

In addition, exploratory endpoints also include several normalization rates. The percentage of subjects normalized will be calculated excluding the subjects who were normalized at Baseline. The definition of normalization is as follows:

- OABSS: 1 point or less on Question 3, or a total score of ≤ 2 points

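### SAP 6.1.3 attaches its 3-day diary condition for hours of undisturbed sleep only to nights with a void, so the per-night values and the Kaplan-Meier analysis have no single diary-length rule

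*SAP*

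**What the plan says.** SAP 6.1.3 derives HUS per night: "hours of undisturbed sleep (HUS) will be calculated by visit and night". It then gives two branches. With a void, HUS runs from sleep onset to the first void. Without one, "HUS is calculated as time from sleep onset time to wake up time". The diary-length condition closes the first sentence and the second opens without it: "only if the diary completed for 3 consecutive days is available. On the other hand, for those subjects who have no micturition episode".

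A further paragraph covers sleep-to-wake intervals over 24 hours. It again places the 3-day condition on the void sentence only, but makes a night without a void missing: "no micturition episode between after sleep onset time and AM.5:59 of the next day, HUS is null".

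Shorter diaries are accepted elsewhere. Protocol 5.3.1: "The diary must be completed for at least 2 days in order to be included in the efficacy assessment for that visit". SAP 6.1.2, for nocturia, whether or not a void occurred: "The diary must be completed for at least 2 consecutive days to allow assessment of night time frequency for at least 1 night".

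SAP 7.4.3 plans two kinds of HUS summary. For the first, "Descriptive statistics for HUS will be derived as the average of 2 consecutive nighttime diary". For the second, Kaplan-Meier, "those subjects who have no micturition episode between sleep onset time and wake up time will be censored at wake up time", with a repeat that treats those subjects as having an event at wake-up. The Kaplan-Meier text states neither a number of nights nor a diary length. SAP 7.10.1 does not impute missing values other than dates of adverse events and concomitant medication.

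**The concern.** Take a man whose diary at a visit covers 2 consecutive days, giving one evaluable night. If he slept through, the no-void sentence gives him a full-night HUS. If he got up to void, the void sentence gives him nothing, because he lacks 3 consecutive days, and nothing is imputed. Whether the value exists then depends on the value itself.

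Records from short diaries would enter only as long, quiet nights. The HUS level would be too high wherever such records are used. A programmer coding the two sentences as written would build this in.

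**Working it through.** **What the text fixes.** SAP 6.1.2 discards data before wake-up on the first day and after sleep onset on the third, so 3 diary days give 2 nights and 2 days give 1. Setting the sections side by side for a 2-day diary:

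- Per-night derivation (6.1.3, interval up to 24 hours): quiet night scored, disturbed night missing.
- Per-night derivation (6.1.3, over 24 hours): both missing. The no-void night is missing whatever the diary length, so this branch does not favour quiet nights.
- Descriptive statistics (7.4.3): 2 consecutive nights are needed, so the 2-day diary drops out either way if the rule is enforced.
- Kaplan-Meier (7.4.3): no rule, so it takes whatever 6.1.3 supplies.

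**Size.** The plan states no HUS figure to reproduce. All four inputs below are assumptions; none is in the documents.

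- f: share of subject-visits with a 2-day diary
- q: probability of a quiet night
- s: HUS on a quiet night; d: HUS on a disturbed night

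Diary length is taken as unrelated to the night, and each subject-visit counts once.

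- Mean under one rule for both branches: T = d + q(s − d)
- Mean under the literal wording: L = [(1 − f)T + f·q·s] / [(1 − f) + f·q]
- Shift: L − T = f·q(1 − q)(s − d) / [(1 − f) + f·q]

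The shift is positive whenever f > 0, s > d and 0 < q < 1. It rises with q only up to roughly q = 0.5.

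With s = 7 h and d = 3 h, the shift in minutes is:

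| f | q = 0.1 | q = 0.2 | q = 0.3 | q = 0.5 |
|---|---|---|---|---|
| 2% | 0.4 | 0.8 | 1.0 | 1.2 |
| 5% | 1.1 | 2.0 | 2.6 | 3.1 |
| 10% | 2.4 | 4.2 | 5.4 | 6.3 |
| 20% | 5.3 | 9.1 | 11.7 | 13.3 |

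Example, f = 20% and q = 0.5: 0.2 × 0.25 × 4 / (0.8 + 0.1) = 0.222 h = 13.3 min.

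With s = 7.5 h, d = 3 h and f = 5%, 10%, 20%, the shift is 2.3, 4.7, 10.3 min at q = 0.20 and 3.2, 6.6, 14.1 min at q = 0.35.

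**Kaplan-Meier.** The share of scored records that are quiet becomes q / [(1 − f) + f·q]. For q = 0.20 it is 0.20/0.984 = 20.3% at f = 2% and 0.20/0.84 = 23.8% at f = 20%. The extra quiet records stay at risk until wake-up, so they raise the curve in both versions of the analysis.

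**Difference between arms** (s = 7 h, d = 3 h).

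- Same f in both arms, q = 0.2 against 0.3: the true difference is 0.1 × 4 = 0.40 h. The literal wording gives 4.217 − 3.813 = 0.404 h at f = 2% and 4.395 − 3.952 = 0.443 h at f = 20%.
- No true difference (q = 0.2 in both arms), 2-day diaries in one arm only: a spurious 0.013 h at f = 2% and 0.152 h at f = 20%.

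**The case against.** The strongest reply is that SAP 7.4.3 already governs the means. Two consecutive nights need 3 diary days, and the worked example there averages one night with a void and one without, so both kinds fall under the same rule. If that rule is enforced, the bias in the means from this source is zero. A reader might infer from 6.1.3 alone that the HUS means are inflated at every visit; with 7.4.3 in view, the documents do not support that. Enforcement is not certain, however. Section 7.4.3 does not say that a subject with one scored night is set to missing, and its averaging sentence follows a restricted analysis of subjects with a night void, which leaves its scope unclear.

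It can also be said that the 3-day condition was meant for both sentences and that the contrast between them concerns only where the interval ends. That is a fair reading, and it is the one that agrees with 7.4.3, so a deliberate outcome-dependent rule is not established. Against it, the condition is placed on the void sentence twice, and where the authors wanted a no-void night missing they said so explicitly.

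Three further limits stand. HUS is exploratory, and 7.4.3 names no between-arm test for it. Staff must review each diary for completeness (Protocol Schedule of Assessments, note j), which may keep 2-day diaries rare. SAP 7.10 refers to a data specification document that is not among the documents reviewed and may settle the point.

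**Conclusion.** The concern holds as a drafting gap with a known direction. Sections 6.1.3 and 7.4.3 do not together give one reproducible diary-length rule for HUS, and the literal wording makes missingness depend on the outcome. The clear exposure is the per-night derivation and the Kaplan-Meier analysis. The descriptive means are exposed only if the 2-night average is not enforced.

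Under the assumed inputs the HUS level is too high by about 0.4 to 14 minutes, calculated as a mean over scored subject-visits with 2-day diaries at 2% to 20%. The true share is unknown, and the shift is small if that share is small.

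A reader might go on to infer that the treatment comparison is distorted. With equal shares of 2-day diaries the assumed 0.40 h difference moves by at most 0.043 h; a material spurious difference needs imbalance between arms, which nothing in the documents suggests. The primary endpoint is not affected.

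**What to change.** Before unblinding, state one diary-length condition in SAP 6.1.3 that covers both the void and the no-void branch, and repeat it for the Kaplan-Meier analysis in 7.4.3. State also in 7.4.3 what happens to a subject-visit with only one scored night.

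The simplest choice is 3 consecutive days for both branches, because it already fits the 2-night average. It costs a sentence in each section, a small programming change, and the quiet nights from 2-day diaries that the literal wording would have kept.

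The alternative is the nocturia rule of 2 consecutive days and at least 1 night. It keeps more subjects and aligns the diary-length rule with nocturia, but some values would rest on a single, noisier night, and the 2-night wording in 7.4.3 would have to be changed to match. Either choice removes the asymmetry.

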6.1.4 Other Efficacy Variables

Not available.

6.2 Safety Variables

Safety will be assessed by evaluation of the following variables:

- Incidence and severity of treatment emergent adverse events (TEAEs)
- Laboratory parameters (serum chemistry, hematology and urinalysis)
- Vital signs: sitting systolic and diastolic blood pressure and pulse rate (home based self-measurements and office measurements)
- Post-void residual (PVR) urine volume
- Maximum urine flow rate (Qmax)

TEAE is defined as an adverse event observed after starting administration of study drug. If the adverse event occurs on Day 1 and the onset check box is marked “Onset after first dose of study drug for the treatment period” or the onset check box is left blank, then the adverse event will be considered treatment emergent. If the adverse event occurs on Day 1 and the onset check box is marked “Onset before first dose of study drug for the treatment period”, then the adverse event will not be considered treatment emergent. If a subject experiences an event both during the screening period and during the treatment period, the event will be considered as TEAE only if it has worsened in severity (i.e. it is reported with a new start date). All adverse events collected that occur within 7 days after taking the last dose of study drug will also be counted as TEAE.

A drug-related TEAE is defined as any TEAE with at least a possible relationship as assessed by the investigator, with ‘not assessable’ or with missing assessment of the causal relationship to both or either one of Mirabegron/Placebo and Tamsulosin.

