5 TREATMENTS AND EVALUATION

5.1 Dosing and Administration of Study Drug(s) and Other Medication(s)

5.1.1 Dose/Dose Regimen and Administration Period

Screening Period:

During the 4-week Screening period, all subjects will receive 1 tamsulosin 0.2 mg tablet along with 1 mirabegron 50 mg matching placebo tablet once daily after breakfast.

Treatment Period:

During the 12-week Treatment period, all subjects will receive their randomized treatment (1 mirabegron 50 mg tablet or 1 matching placebo tablet) along with 1 tamsulosin 0.2 mg tablet, to be taken once daily after breakfast.

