5.1.5 Restrictions During the Study

(1) Medication

When prescribing the study medication, the Investigator or Sub-investigator will explain to the subjects how to take the study medication, with emphasis on the following:

- The subject should take the study medication with water, once daily after breakfast.
- The subject should start taking the prescribed study medication on the day following dispensing of the study drug(s).
- The subject should return any unused study medication at the next visit, and report their compliance to the Investigator or Sub-investigator.
- If the subject has discontinued taking the study medication at his/her own discretion, he/she must visit the study site at the earliest possible time to undergo examination by the Investigator or Sub-investigator.

(2) Micturition diary

The Investigator or Sub-investigator will provide each subject with a micturition diary, after entering into the diary the date of the next scheduled visit, the dates on which the diary should be completed, and the subject number. When providing the micturition diary to the subject, the Investigator or Sub-investigator will explain to the subject how to complete the micturition diary, with emphasis on the following:

- As a rule, the subject will complete the micturition diary during the 3 days immediately before each of the scheduled visits (i.e., at Visits 2, 3, 4, and 5/End of Treatment. Each diary day starts at 06:00 and ends at 05:59 on the following day.
- For the 3 days of recording in the micturition diary, the subject will record their awakening and bedtime hours; time of each micturition; number of micturition episodes, urgency episodes, urinary incontinence episodes, voided volume, sitting blood pressure (SBP and DBP) and pulse rate with the times of measurements. In addition, the subject will record the time of medication. Voided volume will be recorded at Visits 2, and 5 only.
- Sitting blood pressure and pulse rate will be measured twice consecutively on awakening and before bedtime. The second measured value will be recorded in the patient diary. When measurements on awakening are not possible, these should be taken before taking medication for the day as far as possible.
- The subject should bring their completed micturition diary to the next visit.

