5.5.1.1 Treatment-Emergent Adverse Events (TEAEs)

For the purposes of analysis of the safety data following the completion of the study, a TEAE is defined as follows:

- An AE with onset during the double-blind Treatment period
- An AE with onset during the Screening period, with worsening severity during the double-blind Treatment period

Thus, AEs with onset during the Screening period that either resolved during that period or continued into the double-blind Treatment period with the same or lesser severity will NOT be counted as TEAEs.

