6.3 Other Variables

The following variables will be derived for analysis:

- The duration of exposure in treatment period

For each subject, the Length of Time on study drug in treatment period will be calculated in days, using the following formula:

(‘Date of Last Study Drug Taken in Treatment period’[#] - ‘Date of First Study Drug Taken in Treatment period’[#]) + 1

#: These dates can be taken from [Date of Study Drug Taken-page of the Case Report Form]

- The duration of the primary diagnosis (unit: months)

Duration of the primary diagnosis (months) = 12 * (year of visit date of screening visit (Visit 1) – year of Diagnosis) + month of visit date of screening visit (Visit 1) – month of Diagnosis.

If the month for diagnosis is missing, then the month will be imputed by January. As a result, if the duration of primary diagnosis is less than 1 month, then it will be assumed to be 1 month.

If the month and year for diagnosis is missing, then duration of the primary diagnosis is missing.

- Percent overall compliance of the study drug (Mirabegron/Placebo) and Tamsulosin during treatment period

Overall compliance to the dosing schedule will be examined for subjects whose total tablet count of the study drug (Mirabegron/Placebo) and Tamsulosin is known.

Number of tablets which should have been taken depends on the duration of exposure because they should be taken as 1 tablet once daily after breakfast. The following formula can be used for both study drug (Mirabegron/Placebo) and Tamsulosin:

$$\frac{[\text{Total number of tablets consumed during treatment period}]}{[\text{The duration of exposure in treatment period}]} \times 100$$

Where, total number of tablets consumed will be calculated as:

(total number of tablets dispensed) – (total number of tablets returned) – (total number of tablets lost).

- Previous and concomitant medication

Previous medication is defined as medication with at least one dose taken before the date of the first dose of study drug in treatment period.

Concomitant medication is defined as medication with at least one dose taken between the date of first dose (inclusive) and the date of last dose (inclusive) of study drug in treatment period.

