7.10.3 Visit Windows

The day of prescription of the study drug for the treatment period is defined as Day 1, and the following day is defined as Day 2.

As indicated in Section [7.10.2](#), the final handling of outliers will be decided by the time of database lock, and will be based on the opinion and advice of a medical expert. However, the policy described below will be followed as a general rule:

If multiple observed values have been obtained within the same visit window for a subject, the value closest to the scheduled date will be used. If there are similar deviations from the scheduled date, the value obtained on the later date will be used.

Data obtained as early as possible within the allowable range for each visit and within a 7-day period from the final dose will be used.

Micturition Diary:

The mean number of: micturition episodes per 24 hours, urgency episodes per 24 hours, urinary incontinence episodes per 24 hours, urgency incontinence episodes per 24 hours, as well as mean volume voided per micturition and mean number of nocturia episodes will be calculated on the basis of the micturition diary and handled as follows:

The information in the diary (recorded within 3 days before each visit, in principle) measured and recorded in the time windows specified below will be used as the data for that time point.

Time Point	Scheduled Day	Acceptable Time Range
------------	---------------	-----------------------

Diary retrieved at Visit 2	1	Day -7 to Day 1 (AM 5:59)
Diary retrieved at Visit 3	29	Day 19 to Day 36 (AM 5:59)
Diary retrieved at Visit 4	57	Day 47 to Day 64 (AM 5:59)
Diary retrieved at Visit 5	85	Day 75 to Day 92 (AM 5:59)
Diary retrieved at the final evaluation in the Treatment period	The final diary must be completed within 7 days after the last dose of study drug.	
If the subject cannot complete the diary during the 3 days immediately prior to the visit, the diary entries must be recorded for any 3 days within 7 days prior to the visit.		

If for some reason, information cannot be recorded in the diary during the 3 days before a given visit, data will be assessed based on the diary entries recorded within 7 days before the visit and within the above-specified time windows.

OABSS, IPSS, IPSS (QoL), and OAB-q*

The information measured and recorded within the time windows specified below will be used as the data for that time point.

Time Point	Scheduled Day	Acceptable Time Range
Completed at Visit 1	-28	Day -35 to Day -21

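### SAP 6.2 settles pre-dose versus post-dose adverse events on the prescription day (Day 1), while Protocol 5.1.5 starts double-blind dosing the next day, so a blank check box can turn a pre-dose event into a TEAE

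*SAP*

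**What the plan says.** **TEAE rule.** SAP 6.2 opens with a general definition: "TEAE is defined as an adverse event observed after starting administration of study drug". A special rule for Day 1 follows. If the box is marked as after the first treatment-period dose "or the onset check box is left blank, then the adverse event will be considered treatment emergent". If it is marked as before that dose, "then the adverse event will not be considered treatment emergent". No other day has a before/after rule.

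**Day 1.** SAP 7.10.3 states: "The day of prescription of the study drug for the treatment period is defined as Day 1". Protocol 7.8.1 says the same. Neither document defines Day 1 as the day of first dose.

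**First dose.** Protocol 5.1.5 (1) instructs: "The subject should start taking the prescribed study medication on the day following dispensing of the study drug(s". Protocol 5.1.1 has the tablets "to be taken once daily after breakfast". The per-protocol rule on minimum time on drug (Protocol 7.2.2, SAP 5.2.1) also counts from the day after dispensing.

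**Text pointing the other way.** Protocol 7.5.2 places the Visit 2 laboratory tests before dosing at that visit. The key-term definition of the Screening period, in both documents, ends just before drug is given at Visit 2.

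**Protocol's TEAE definition.** Protocol 5.5.1.1 uses a different anchor: "An AE with onset during the double-blind Treatment period", or worsening in that period. The protocol's key terms start the Treatment period at randomization, and footnote d of the Schedule of Assessments places randomization after all other Visit 2 procedures.

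**The concern.** The check box answers a question that arises only on the day of the first dose: did the event start before or after the tablet? The SAP asks it on the prescription day. If the first tablet is taken the next morning, the answer for every Day 1 event is already known, and the blank-box default can only move pre-dose events into the TEAE count. On Day 2, when the question does arise, there is no tie-break.

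The affected output is the TEAE incidence tables and their Fisher's exact comparisons (SAP 7.5.1.1 and 7.5.1.2), which serve the secondary objective of safety and tolerability. SAP 6.2 also counts a TEAE with a missing causality assessment as drug-related. An event with both fields empty would therefore enter the drug-related tables although it arose on single-blind placebo plus tamsulosin.

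**Working it through.** The plan gives no figure for this point, so there is none to reproduce. The check compares the rules and then bounds the size.

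**1. Day arithmetic.** Prescription and dispensing of treatment-period drug = Day 1 (SAP 7.10.3; Visit 2 in the Schedule of Assessments). First dose under Protocol 5.1.5 = Day 1 + 1 = Day 2.

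**2. How each rule treats an event in a man first dosed on Day 2.**

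| Event | SAP 6.2 general definition | SAP 6.2 Day 1 rule | Protocol 5.5.1.1 |
|---|---|---|---|
| Day 1, before randomization, box blank | Not a TEAE | TEAE | Not a TEAE |
| Day 1, after randomization, box blank | Not a TEAE | TEAE | TEAE |
| Day 1, after randomization, marked as before first dose | Not a TEAE | Not a TEAE | TEAE |
| Day 2, before the tablet | Not a TEAE | No rule | TEAE |

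In the first row the default contradicts both definitions. In the second it contradicts the SAP's own definition but agrees with the protocol's. The third and fourth rows show that the two documents' definitions differ whatever is done about the box.

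**3. Share of the TEAE window.** SAP 6.2 adds 7 days after the last dose. With a nominal last dose on Day 85, the window ends on Day 85 + 7 = Day 92.
- From Day 2: 92 − 2 + 1 = 91 days.
- From Day 1: 92 days.
- Excess: 1/91 = 1.1%.

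**4. Number of men, on assumptions.** The documents give neither the run-in adverse event rate nor the share of blank boxes. Suppose a proportion I of men have an event onset during the 28-day run-in at a constant daily rate, and a proportion b of boxes are blank. Then the daily proportion is d = 1 − (1 − I)^(1/28), and the men counted per arm are 275 × d × b.

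| I (assumed) | d | Day 1 onsets per 275 | Counted, b = 5% | Counted, b = 25% | Counted, b = 100% |
|---|---|---|---|---|---|
| 5% | 0.00183 | 0.50 | 0.03 | 0.13 | 0.50 |
| 10% | 0.00376 | 1.03 | 0.05 | 0.26 | 1.03 |
| 20% | 0.00794 | 2.18 | 0.11 | 0.55 | 2.18 |
| 30% | 0.01266 | 3.48 | 0.17 | 0.87 | 3.48 |

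**5. Effect on the comparison.** If a fraction q of each arm has a misclassified event, independently of true TEAEs, an incidence p becomes p + q(1 − p), and a risk difference is multiplied by (1 − q). At the top of the table q = 3.48/275 = 1.3%, so the difference shrinks by about 1.3% of its own size.

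**The case against.** **The first-dose day is not settled.** A reader might infer that no Day 1 event can follow a double-blind dose. The documents do not support so firm a statement. Protocol 7.5.2 and the Screening-period definition can be read as dosing at Visit 2, and on that reading the Day 1 check box works as intended. This stands: the passages conflict and must be reconciled, and this review does not say which dosing day is right. It does not rescue the rule, which is correct on one reading and wrong on the other. A rule tied to the recorded dose date is correct on both.

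**Some Day 1 events are TEAEs under the protocol.** This also stands. Under Protocol 5.5.1.1, onset after randomization is enough. The problem is then a disagreement between the definitions, as well as a default that overrides the SAP's own.

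**Day 2.** A reader might infer that the SAP counts events before the first tablet on Day 2. It does not say so. The general definition applies on every day and excludes an event known to precede the dose. What is missing is a tie-break when the order is unknown.

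**Counting unknown timing as treatment-emergent is conservative.** That is reasonable where timing is in doubt, and it should be kept for the first-dose date. It is not reasonable where the recorded dates already show that no double-blind dose had been taken.

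**Few events will be affected.** This stands. A box marked as before the first dose removes the event. Protocol 8.1.1 requires complete query responses and monitor verification. SAP 7.10 points to a data specification document that is not available here. A reader might guess that as many as 2% of men (11 of 550) are affected. At a constant rate that would need 1 − 0.98^28 = 43% of men with a run-in event and every box blank, which nothing in the documents supports. Nor do the Visit 2 tests make Day 1 events likely: Protocol 5.5.1 counts a test abnormality as an adverse event only if it meets listed criteria.

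**Conclusion.** The point holds as an error in a definition with a small effect. For a subject dosed as Protocol 5.1.5 instructs, SAP 6.2 counts a blank-box Day 1 event as treatment-emergent, contrary to its own opening sentence. The protocol and SAP also anchor TEAEs differently, on randomization and on first dose.

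The misclassification is confined to about one day of a 92-day window and needs a blank or wrongly marked box. Because it precedes double-blind dosing and the box is completed blind, it should affect both arms alike. It would raise both incidences slightly and dilute the comparison by about 1%. The illustrative range of about 0.03 to 3.5 men per arm rests on assumed run-in incidences of 5% to 30%, a constant daily rate and blank-box shares of 5% to 100%. No efficacy result is touched. The correction is worth making because the TEAE flag underlies most of the safety tables and changing it after unblinding would be open to challenge.

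**What to change.** In SAP 6.2, replace Day 1 with the recorded CRF date that SAP 6.3 calls "Date of First Study Drug Taken in Treatment period" (SAP 7.5.1 already uses the first administration date for date imputation). Apply the check box, including the blank-box default, only to events on that date. Classify earlier onsets as pre-treatment unless they worsen later. This also supplies the missing tie-break, and it works whichever day a man starts.

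At the same time:
- Align the TEAE definitions in Protocol 5.5.1.1 and SAP 6.2, and state which anchor the tables use.
- Reconcile Protocol 5.1.5, Protocol 7.5.2 and the Screening-period definition on when double-blind dosing starts.
- State how the revised rule treats events with partial dates. SAP 7.5.1 moves an imputed onset that falls before the first dose to the first-dose date, and SAP 7.10.1 lets imputed dates decide treatment emergence.

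The core change costs one sentence and a small programming edit, with no new data. It should be made before unblinding, when SAP section 1 has the plan finalized. The downside is that TEAE counts may fall slightly. Events after randomization but before the first dose would also cease to be TEAEs, although Protocol 5.5.1.1 counts them; the SAP should state that departure and could list those events separately.
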